E3.1. Secondary Aim#1: Determine whether prehospital tranexamic acid as compared to placebo reduces the incidence of hyperfibrinolysis (estimated percent lysis > 7.5%), acute traumatic coagulopathy (ATC, presenting INR > 1.4), improves PT measurements and additional r-TEG parameters, D-dimer levels, activated Protein C levels, and plasmin-antiplasmin complexes.

Secondary Hypothesis 1: Prehospital tranexamic acid as compared to placebo will reduce the incidence hyperfibrinolysis (estimated percent lysis > 7.5%), reduce the incidence of patients with an arrival INR > 1.4, improve PT and additional presenting r-TEG parameters of coagulopathy including ACT, r-value, k-time, α -angle, maximal amplitude (MA) and G-values and D-dimer levels, activated Protein C levels and plasmin-antiplasmin complexes.

E.3.2. Secondary Aim#2: Determine whether prehospital tranexamic acid as compared to placebo results in a lower incidence of 24 hour mortality, acute lung injury, multiple organ failure, nosocomial infection, early seizures, pulmonary embolism, shock parameters and early resuscitation and transfusion requirements.

Secondary Hypothesis 2A: Prehospital tranexamic acid as compared to placebo will reduce the incidence of 24 hour and 30 day mortality, acute lung injury, multiple organ failure, nosocomial infection, early (24hr) seizures and in-hospital pulmonary embolism.

Secondary Hypothesis 2B: Prehospital tranexamic acid as compared to placebo will improve presenting base deficit, 24 hour crystalloid requirements and reduce 6 hour and 24 hour blood and blood component transfusion requirements (PRBC, FFP and platelets).

E.3.3. Secondary Aim #3: To investigate potential novel mechanisms by which tranexamic acid alters the inflammatory response to injury independent of effects on hyperfibrinolysis. Investigations of the effects of tranexamic acid on inflammation will include analysis of platelet and leukocyte activation via flow cytometry, measurements of plasmin levels and subsequent plasmin mediated complement activation and the early inflammatory cytokine response to trauma.

Secondary Hypothesis 3A: Prehospital tranexamic acid as compared to placebo will reduce plasmin levels and markers of platelet and leukocyte activation measured by flow cytometry (FACS) and result in a plasmin mediated reduction of complement activation as measured by C3a and Factor B levels.

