i. At scene of injury or during emergency medical transport

ii. Documented at referring hospital prior to emergency medical transport arrival

H.2.2 Specific Exclusion Criteria:

1. Age > 90 or < 18 years of age; **2.** Inability to obtain intravenous or intraosseous access;**3.**

Documented (radiographic evidence) cervical cord injury with motor deficit; **4.** Known prisoner; **5.**

Known pregnancy; **6.** Traumatic arrest with > 5 minutes CPR without return of vital signs; **7.**

Penetrating cranial injury **8.** Traumatic brain injury with brain matter exposed; **9.** Isolated drowning or

hanging victims **10.** Wearing an opt out bracelet. **11.** Objection to study voiced by subject or family

member at the scene. **12.** Isolated fall from standing

Inclusion and exclusion criteria will be assessed based on available information at the time of enrollment. Although all reasonable efforts will be made by the emergency medical crew to either directly witness or obtain documentation of inclusion criteria, including qualifying vitals, due to the nature of the emergency pre-hospital setting, there may be occasions where the emergency medical crew must rely on verbal report of qualifying vitals from the referring hospital or ground crew. In these instances, if, after subsequent review of outside hospital and/or ground crew documentation, it is determined that the subject did not meet inclusion criteria

and/or met exclusion criteria, the subject will remain enrolled in the study based on the intention-to-treat principle.

In the event that a verbal report must be used in lieu of physical documentation or directly witnessing the qualifying vitals, documentation of the verbal report will serve as the source documentation for determining eligibility. Verbal reports will be documented in the emergency medical record and will detail the information reported and by whom.

H.3. Interventional Arm: The Intervention will have both a prehospital phase and in-hospital phase. Investigational Drug Services (IDS) at the University of Pittsburgh will be utilized to supply and organize both tranexamic acid and placebo along with respective normal saline bolus and infusion bags to all participating trial sites. IDS at the University of Pittsburgh has a long track record of managing large multicenter trials and is currently executing and responsible for over 150 inpatient and outpatient clinical trials.

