I.2 Secondary Clinical Outcomes: Secondary clinical outcomes will include the incidence of hyperfibrinolysis (EPL > 7.5% by rapid-TEG analysis) upon arrival to the trauma bay within the first 6 hours, the incidence of acute traumatic coagulopathy (INR > 1.4), 24 hour mortality, acute lung injury, multiple organ failure, the development of nosocomial infection, early (24hr) seizures, in-hospital pulmonary embolism, presenting base deficit, 24 hour crystalloid requirements and 6 hour and 24 hour blood and blood component transfusion requirements (PRBC, FFP and platelets). *These same clinical outcomes will similarly be used for the randomized tranexamic acid dosage regimen comparison.*

I.3. Secondary Laboratory/Mechanistic Outcomes: All laboratory/mechanistic outcomes will be measured during the first 6 hours from trauma center arrival and at 12 and 24 hours (+/- 12 hours) out from injury. Those laboratory/mechanistic outcomes including flow cytometry which require fresh blood samples will be performed only at the University of Pittsburgh on a subset of patient samples unless participating centers have specific capabilities and following appropriate training for standardization. *These same laboratory/mechanistic outcomes will similarly be used for the randomized tranexamic acid dosage regimen comparison at 12 and 24 hours post-injury.*

I.4. Clinical Outcomes Methods/Definitions: All clinical outcomes will be prospectively evaluated for throughout ICU and hospital admission and the timing from the day of initial injury will be recorded for time-to-event statistical analysis.

I.4.1. 30 day and 24 hour mortality: 30 day mortality will be prospectively recorded from the day of trauma bay arrival. Over the first 24 hours we will document and record the time of death in hours. We suspect that patients enrolled will have a significant percentage of mortality that occurs in the first 24hrs.

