I.5. Laboratory/Mechanistic Outcome Methods/Definitions: All measurements will be performed within 6 hours of arrival and at 12 and 24 hours post injury (+/- 12 hours) for the randomized dosage regimen comparison. One more additional blood sample will be collected at 72 hours (\pm 12 hrs) for D-dimer, activated Protein C levels and plasmin-antiplasmin complexes measurements. Excluding r-TEG analysis and PT/ INR measurements, all blood and serum samples will be spun, stored and batched at their respective institution and delivered to the University of Pittsburgh where formal ELISA immunoassay measurements will be undertaken. Those laboratory/mechanistic outcomes including flow cytometry which require fresh blood samples will be performed only at the University of Pittsburgh on a subset of patient samples unless participating centers have specific capabilities and following appropriate training for standardization.

I.5.1. Coagulopathy and TEG parameters (Aim#2): To appropriately characterize differences in coagulopathy between tranexamic acid and placebo, in addition to r-TEG measurements of hyperfibrinolysis, presenting PT/ INR and additional TEG parameters will also be measured (ACT, r-value, k-time, α -angle, maximal amplitude, and G-values). All rapid TEG measurements will be performed within 6 hours of arrival and at 12 and 24 (+/- 12 hours) hours post injury. TEG analysis will be performed on a TEG[®] 5000 Thromboelastograph[®] Hemostasis Analyzer which will reside within the emergency department of each participating site. Standard laboratory INR will be drawn and measured at each institution within 6 hours of arrival and at 12 and 24 hours (+/- 12 hours). To further quantify the coagulopathy and hyperfibrinolysis post injury in these patients, D-dimer, activated Protein C levels and plasmin-antiplasmin complexes will be measured by ELISA plate assay. (ANIARA, USCN Life Science Inc., DRG International, Inc.) Plasmin-antiplasmin complexes may represent a more common, subclinical measurement of fibrinolytic activity that is not able to be assessed using standard TEG analysis, but elevated levels are associated with significantly worse outcome post injury and may be a marker than demonstrates the mechanism by which tranexamic acids has it beneficial effects.

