The overarching goal of the study proposal is to assess the efficacy of prehospital tranexamic acid as compared to placebo for injured patients at risk for traumatic hemorrhage who require emergency medical transport. Additional goals include dose regimen comparison and characterization of the mechanisms responsible for tranexamic acid's beneficial effects. All primary and secondary analyses will be performed based on the Intent-to-Treat principle for the prehospital randomization and analyses will include all enrolled patients grouped by randomization assignment.

J.1. Data Analysis for Primary Outcome: We follow an intent-to-treat approach in analyzing our primary outcome of 30 day mortality.

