
J.2. Analysis of Prehospital Randomized Secondary Outcomes: Unless there is sufficient power (predetermined before the analysis is begun), the approach to analysis of secondary endpoints will generally be calculation of confidence limits on intervention group differences or model parameters rather than formal tests of significance at a specified critical level as the trial will not have sufficient power to detect difference in all of these outcomes. However, these comparisons will add to the knowledge of the benefits and risks of the interventions. Parametric and nonparametric comparisons will be applied according to normalcy. All tests used will be two-tailed tests at significance level (α) of 0.05. For prehospital randomized clinical outcomes we will use Chi-square with 95% confidence intervals for dichotomous outcomes and parametric or non-parametric testing for continuous variable with 95% confidence intervals. For prehospital randomized laboratory or exploratory outcomes we will use parametric or non-parametric testing for continuous variable with 95% confidence intervals.

J.3. Analysis for Second Stage In-hospital Randomized Dosage Regimens: Chi-square test will be able to test the effect of different tranexamic dosage regimens on hyperfibrinolysis. Similarly, chi-square will be used to detect any differences between dosage groups for 30 day mortality. To detect a trend in dosage response, test for trend will be implemented. As additional analysis and to account for site and to adjust for some important covariates, we will use logistic regression to test the effect of dosage on hyperfibrinolysis. Similarly Cox proportional hazards regression can be used for 30 day mortality. *For In-hospital randomized dosage regimen comparison for clinical outcomes* we will use Chi-square with 95% confidence intervals for dichotomous outcomes and parametric or non-parametric testing for continuous variable with 95% confidence intervals. *For In-hospital randomized dosage regimen comparison for laboratory or exploratory outcomes* we will use parametric or non-parametric testing for continuous variable with 95% confidence intervals.

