J.4. Predefined Subgroup Analyses: Predefined subset analyses will be performed looking at 1.) patients who ultimately did or did not required blood transfusion 2.) those patients with significant traumatic brain injury (Head AIS >2) versus those without significant brain injury (Head AIS ≤ 2), 3.) those patients enrolled from the scene of injury versus those enrolled from a referral hospital, 4.) those patients that require operative intervention in the first 24 hours, 5.) those patients with a preinjury history of vitamin K antagonist medication history versus those without, 6.) those patients with preinjury history of antiplatelet medication history. 7.) those patients who ultimately did or did not require massive transfusion (≥ 10 units blood in first 24hrs). It is recognized that the study is not appropriately powered for these subgroup comparisons and the results and conclusions formulated from these subgroup analyses will be considered exploratory in nature and will not be used as a basis for treatment recommendations.

J.5. Randomization of Ineligible Subjects: It is anticipated that there will be a small proportion of patients enrolled who receive either tranexamic acid or placebo that in retrospect will not have met the entry criteria and are thus ineligible. In this circumstance, patients will be analyzed according to the group to which they were randomized. Subgroup analyses based on eligibility criteria will be performed if the number of patients so affected is large. However, based on the relatively limited inclusion and exclusion criteria it is anticipated that the frequency of this event will be low.

J.6. Non-adherence: In some circumstances, patients may receive the incorrect treatment packet. Non-adherence is most likely to occur in the case of the exsanguinating patient when time is limited and the wrong treatment pack is utilized. Fortunately, this event is relatively rare. In keeping with the intention-to-treat analytic design, these patients will be analyzed with the group to which they were to be randomized to.

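### The INR > 1.4 outcome counts vitamin K antagonist users with an already raised INR as traumatic coagulopathy, which dilutes this secondary comparison

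*Combined protocol and SAP*

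**What the plan says.** Section I.2 includes "the incidence of acute traumatic coagulopathy (INR > 1.4") among the secondary clinical outcomes and applies the same outcomes to the dosing comparison. Secondary Aim 1 (E.3.1) specifies the presenting value: "acute traumatic coagulopathy (ATC, presenting INR > 1.4"). Secondary Hypothesis 4A (E.3.4) uses INR > 1.4 again at 12 hours from arrival. Under I.5.1, "Standard laboratory INR will be drawn and measured at each institution within 6 hours of arrival", and again at 12 and 24 hours.

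H.2.2 has twelve exclusions. The age limit is "Age > 90 or < 18 years of age", and anticoagulant use is not on the list. J.4 names as a predefined subgroup "those patients with a preinjury history of vitamin K antagonist medication history versus those without", so the plan expects users, but it adds that "the study is not appropriately powered for these subgroup comparisons" and treats the results as exploratory.

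The opening of section J says that "analyses will include all enrolled patients grouped by randomization assignment". For dichotomous clinical outcomes J.2 states: "we will use Chi-square with 95% confidence intervals for dichotomous outcomes". No stratification or adjustment for anticoagulant history is given. J.3 repeats the chi-square for the dosing regimens. Its covariate-adjusted regressions are for hyperfibrinolysis and 30-day mortality, not for INR > 1.4.

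**The concern.** The outcome is meant to capture coagulopathy caused by the injury, and the hypothesis is that tranexamic acid reduces it. A vitamin K antagonist raises the INR by design. That is general pharmacology and is not stated in the documents, so it enters here as an assumption. A user already above 1.4 before injury scores as a case in either arm.

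Two things follow. The reported incidence mixes drug effect with injury effect. The arm difference shrinks by the user share, because users add the same number of expected cases to both sides. A real effect on presenting INR could then look smaller and less precise than it is. The plan takes this kind of care elsewhere: I.4.3 keeps surgical site infections out of the principal infection outcome because operations would confound it.

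**Working it through.** **Inputs from the documents.** 497 per arm, two-sided alpha 0.05 and a pooled-variance z test (K.1, for the primary outcome). Coagulopathy in over 25% of patients at trauma admission (C.2). The documents give no user share, no INR distribution in users, and no effect size or power for INR > 1.4.

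**Check of the formula on the plan's own figure.** Power = Φ[(d − 1.96·SE0)/SE1], with SE0 = √(2·p̄(1−p̄)/n) and SE1 = √((pC(1−pC) + pT(1−pT))/n). For 16% v 9.65%, d = 0.0635, SE0 = 0.02121 and SE1 = 0.02112. Then (0.0635 − 0.04157)/0.02112 = 1.04 and power is 0.850, as K.1 states.

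**Assumptions for INR > 1.4.** Among non-users, 25% on placebo and 18% on tranexamic acid. C.2 does not restrict its 25% to non-users, and the 18% is illustrative. Let f be the user share and s the proportion of users above 1.4, equal in both arms.

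**Observed rate in each arm** = f·s + (1−f)·p. The difference is therefore (1−f) × 7 points.

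**Worked case, f = 5%, s = 1.**
- Placebo: 0.05 + 0.95 × 0.25 = 0.2875. Tranexamic acid: 0.05 + 0.95 × 0.18 = 0.2210. Difference 0.0665.
- All patients, n = 497: SE0 = 0.02762, SE1 = 0.02754, (0.0665 − 0.05413)/0.02754 = 0.449, power 67%.
- Non-users only, n = 497 × 0.95 = 472: SE0 = 0.02674, SE1 = 0.02664, (0.0700 − 0.05241)/0.02664 = 0.660, power 75%.
- Users' share of placebo-arm cases: 0.05/0.2875 = 17%.

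| User share | Rates, all patients | Difference (points) | Power, all patients | Power, non-users only | Users among placebo-arm cases |
|---|---|---|---|---|---|
| 1% | 25.75% v 18.82% | 6.93 | 75% | 76% | 4% |
| 2% | 26.50% v 19.64% | 6.86 | 73% | 76% | 7.5% |
| 5% | 28.75% v 22.10% | 6.65 | 67% | 75% | 17% |
| 10% | 32.50% v 26.20% | 6.30 | 59% | 72% | 31% |

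**Other assumptions.** With 20% v 14% in non-users and 10% users, power is 50% v 67%. If only 80% of users exceed 1.4 (25% v 18% again), it is about 68% v 75% at 5% users and 61% v 72% at 10%.

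**Interval scale.** The 95% half-width is 1.96 × SE1. At 5% users the all-patient result is 6.65 ± 5.40 points, against 7.00 ± 5.22 in non-users. At 2% it is 6.86 ± 5.22 against 7.00 ± 5.14.

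**Why stratifying helps.** A stratum in which everyone is a case adds nothing to the numerator or the variance of the Mantel-Haenszel statistic. With s = 1, the stratified test on all patients therefore carries the same information as the non-user comparison. A common risk difference averaged over strata is still diluted by users, so the non-user estimate needs to stand beside it.

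**The case against.** The strongest objections concern size and status, and most of them stand.

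- **The size is unknown.** Nothing in the documents shows whether users are 1% or 10% of enrolment. At 1% the loss is about 1.5 points of power.
- **Power is a weak yardstick here.** J.2 says secondary endpoints will generally get confidence limits rather than formal tests. No power is stated for this outcome, so none that was promised is lost. The change in the interval is modest.
- **The all-patient contrast is valid.** Randomisation balances users in expectation. The dilution is non-differential and conservative.
- **J.4 already foresees a user v non-user split.** It is exploratory, however, and J.4 does not say which outcomes it covers, so the headline result stays the mixed one.

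A reader might infer that the main endpoint of Secondary Hypotheses 1 and 4A is spoiled. The documents do not support that. Both hypotheses put hyperfibrinolysis first, and INR > 1.4 is one marker among r-TEG parameters, D-dimer, activated protein C and plasmin-antiplasmin complexes. Hypothesis 4A also concerns the 12-hour INR in three groups of about 166 (497/3). The figures above do not apply to it, and users may not stay above 1.4 that long once in-hospital resuscitation and transfusion (H.8) have begun.

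A reader might also infer that users should be dropped from the main comparison. That would depart from the all-enrolled rule in section J. It would also rest on a history that may be obtained after randomisation, since section M describes patients as often unable to respond, and N.2 and N.3 do not name medication history as a data item.

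**Conclusion.** The point holds as a minor one. The definition makes no allowance for pre-injury vitamin K antagonist use, users are eligible and expected, and the planned comparison is an unstratified chi-square. If users arrive with an INR already above 1.4, incidence is overstated and the difference shrinks by the user share. Under the assumptions shown, the power forgone is about 1.5 points at 1% users, 3 at 2%, 7 at 5% and 13 at 10%. These figures rest on an assumed user share, assumed rates in non-users and all users exceeding 1.4; only the direction follows without choosing a user share. Type I error, the sample size and the 30-day mortality analysis are untouched.

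**What to change.** In J.2, keep all enrolled patients but replace the plain chi-square for presenting INR > 1.4 with a comparison stratified by pre-injury vitamin K antagonist history, for example Mantel-Haenszel. Pre-specify the estimate in non-users alongside it, rather than leaving it to the exploratory J.4 subgroup. Do the same in J.3 for the dosing comparison, with the version of the test for three groups. Report the number of users by arm.

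Confirm that the history is a named data field. It should come from pre-injury sources, be recorded blind to arm, and not be inferred from the study INR.

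The cost is a few lines of text and a little more analysis. The non-user estimate uses slightly fewer patients, by the user share, and both analyses depend on a complete medication history.

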Secondary Hypothesis 3B: Prehospital tranexamic acid as compared to placebo will attenuate trauma-induced pro-inflammatory changes and immunosuppression by reducing the early inflammatory cytokine response (GM-CSF, IFN- γ , IL-1 β , IL-2, IL-4, IL-5, IL-6, IL-8, IL-10 and TNF- α), HMGB1 levels and early inflammatory gene responses as measured by RT-PCR.

E.3.4. Secondary Aim#4: Determine whether different dosing regimens of tranexamic acid upon arrival in the hospital are associated with improvements in hyperfibrinolysis, markers of coagulopathy, clinical outcomes, platelet and leukocyte activation and the early inflammatory response.

Secondary Hypothesis 4A: Repeat dosing of 1 gram of tranexamic acid followed by 1 gram over approximately 8 hours after hospital arrival in patients who have already received 1 gram of prehospital tranexamic acid will lower the incidence of 12 hour (from arrival) hyperfibrinolysis (estimated percent lysis > 7.5%), coagulopathy (INR > 1.4) and improve r-TEG markers of coagulopathy, D-dimer levels, activated protein C levels and plasmin-antiplasmin complex levels as compared to standard dosing of tranexamic acid (1 gram over approximately 8 hours) or abbreviated dosing (no additional tranexamic acid).

Secondary Hypothesis 4B: Repeat dosing of 1 gram of tranexamic acid followed by 1 gram over approximately 8 hours after hospital arrival in patients who already received prehospital tranexamic acid will lower the incidence of 24 hour and 30 day mortality, acute lung injury, multiple organ failure and nosocomial infection as compared to standard dosing or abbreviated dosing.

Secondary Hypothesis 4C: Repeat dosing of 1 gram of tranexamic acid followed by 1 gram over approximately 8 hours after hospital arrival in patients who already received prehospital tranexamic acid will reduce 12 hour (from arrival) base deficit, 24 hour crystalloid requirements and 6 hour and 24 hour blood and blood component transfusion requirements (PRBC, FFP and platelets) as compared to standard dosing or abbreviated dosing.

Secondary Hypothesis 4D: Repeat dosing of 1 gram of tranexamic acid followed by 1 gram over approximately 8 hours after hospital arrival in patients who already received prehospital tranexamic acid will reduce 12 hour and 24 hour (from arrival) markers for platelet and leukocyte activation, plasmin

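### Section I.2 carries arrival hyperfibrinolysis and presenting base deficit into the in-hospital dose comparison, against the 12-hour endpoints of Hypotheses 4A and 4C; no 12-hour base deficit outcome is defined

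*Combined protocol and SAP*

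**What the plan says.** - **I.2 (Secondary Clinical Outcomes)** defines one outcome as "the incidence of hyperfibrinolysis (EPL > 7.5% by rapid-TEG analysis) upon arrival to the trauma bay within the first 6 hours". It also lists "in-hospital pulmonary embolism, presenting base deficit, 24 hour crystalloid requirements" in the same sentence. It closes with "These same clinical outcomes will similarly be used for the randomized tranexamic acid dosage regimen comparison" and gives no new time point. INR > 1.4 is listed without a time; Secondary Aim 1 ties it to presentation.
- **Hypothesis 4A (E.3.4)**: repeat dosing "will lower the incidence of 12 hour (from arrival) hyperfibrinolysis (estimated percent lysis > 7.5"%), and the same hypothesis covers INR > 1.4.
- **Hypothesis 4C (E.3.4)**: repeat dosing "will reduce 12 hour (from arrival) base deficit, 24 hour crystalloid requirements" and transfusion requirements.
- **H.3.2** describes blood sampling on arrival, allows the arrival rapid TEG up to 6 hours, and then describes eligibility verification and the second-stage regimen (Bags B and C). It does not fix the start of Bag B relative to the arrival draw.
- **I.3, I.5 and I.5.1** schedule laboratory measurements, including rapid TEG and INR, at 12 and 24 hours after injury with a 12-hour tolerance. I.3 and I.5 link the later measurements to the dose comparison.
- **J.3**: "Chi-square test will be able to test the effect of different tranexamic dosage regimens on hyperfibrinolysis". It adds a test for trend and a logistic model, and names no sampling time.
- **N.3** lists base deficit among the in-hospital data without a time.

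**The concern.** The second randomisation applies only to patients who have all had the same 1 gram before hospital. Until Bag B starts, the three regimens differ only by chance. A value drawn by then is a baseline for this comparison and cannot respond to it. An analyst who takes the outcome definition from I.2 would compare the regimens on exactly such values.

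The dose comparison is Aim 4. At stake is a null result on hyperfibrinolysis or base deficit that carries no information about dose but can be read as showing no dose difference. Because J.3 leaves the hyperfibrinolysis sample unnamed, the choice could also be made after the data are seen.

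**Working it through.** **1. The passages side by side**

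| Endpoint for the dose comparison | I.2 | Hypotheses 4A/4C | Scheduled measurement | J.3 |
|---|---|---|---|---|
| Hyperfibrinolysis (EPL > 7.5%) | arrival, within 6 h | 12 h from arrival | within 6 h of arrival; 12 and 24 h after injury (I.5.1) | no time |
| INR > 1.4 | no time | 12 h from arrival | within 6 h of arrival; 12 and 24 h (I.5.1) | not named |
| Base deficit | presenting | 12 h from arrival | none at 12 h; N.3 gives no time | not named |

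I.3 ends with a sentence parallel to the one in I.2 but adds the 12- and 24-hour times. I.2 has no such addition. The hyperfibrinolysis row contradicts itself but has a usable later sample. The base deficit row has no later sample at all.

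**2. The later sample's own timing**

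The schedule counts from injury; 4A and 4C count from arrival. If the tolerance applies to the 12-hour draw, its window is 12 − 12 = 0 to 12 + 12 = 24 hours after injury. A draw could meet the schedule and still precede the regimen.

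**3. What early samples do to the three-regimen test**

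The plan's figure used here is 497 per arm. It reproduces: with a pooled-variance two-sided z test at 0.05 and control mortality of 0.16, power is 0.900, 0.851 and 0.800 at treated rates of 0.0919, 0.0965 and 0.1003, against the stated 0.90, 0.85 and 0.80. Nothing in this point changes those figures. An equal three-way split gives 497/3 = 165.7, about 166 per regimen.

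The documents give no hyperfibrinolysis rate or dose effect, so the following is an illustration. Assume a rate p in two regimens, halved to p/2 under repeat dosing. If a share f of samples is too early to be affected, the repeat-dose rate observed is p − (p/2)(1 − f). For the chi-square test on 2 degrees of freedom, with alpha 0.05 taken from J.2 because J.3 states none:

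noncentrality = n × Σ(pᵢ − p̄)² / [p̄(1 − p̄)]

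Worked for p = 0.10:

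- f = 0: rates 0.05, 0.10, 0.10; p̄ = 0.0833; Σ = 0.001667; noncentrality = 165.7 × 0.001667 / 0.0764 = 3.61; power 0.38.
- f = 0.5: rates 0.075, 0.10, 0.10; p̄ = 0.0917; Σ = 0.000417; noncentrality = 165.7 × 0.000417 / 0.0833 = 0.83; power 0.12.
- f = 1: rates equal; noncentrality 0; rejection probability 0.05.

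| Assumed rate p | all samples after the regimen acts | half too early | all too early |
|---|---|---|---|
| 5% | 0.20 | 0.08 | 0.05 |
| 10% | 0.38 | 0.12 | 0.05 |
| 20% | 0.72 | 0.21 | 0.05 |
| 30% | 0.91 | 0.33 | 0.05 |

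Only the last column is free of the assumed rates and effect: with no exposure difference at sampling, the test rejects at alpha. The same holds for any valid test across regimens on a presenting base deficit drawn before Bag B.

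**The case against.** The strongest reply is that the plan handles hyperfibrinolysis and INR elsewhere. I.5.1 schedules rapid TEG and INR at 12 and 24 hours, I.5 assigns its measurements to the dose comparison, 4A names 12 hours, and J.3, naming no time, does not contradict 4A. On that reading the sentence in I.2 is loose drafting. This stands as far as it goes: a post-arrival sample exists and may well be the one intended. It does not remove the conflict, because I.2 is where hyperfibrinolysis is defined as an outcome and where its reuse is stated.

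A reader might infer more than the documents support:

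- *That the J.3 test is certain to use arrival values and so has power equal to alpha.* This needs the arrival value to be the one analysed and every draw to precede Bag B. Neither is established. The arrival TEG window runs to 6 hours in H.3.2 (60 minutes in the DSMB charter), so some arrival samples may fall during the regimen.
- *That all the outcomes reused from I.2 are affected.* Mortality, lung injury, organ failure, infection, embolism and transfusion accrue after arrival.
- *That adjusting for the arrival value would recover a known amount of power.* For a continuous marker the variance falls by the squared correlation: 9%, 25% or 49% at assumed correlations of 0.3, 0.5 or 0.7. The documents give no correlation, and the gain does not carry over to a chi-square test on a binary outcome. The covariates left open in J.3 do not exclude the arrival value either.

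The reply has no answer for base deficit.

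**Conclusion.** The point holds in two parts of different strength.

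- **Base deficit:** the endpoint of Hypothesis 4C is undefined. The only base deficit outcome is the presenting value, which, on the order of events in H.3.2, is normally drawn before the second-stage regimen. A comparison on it cannot inform the dose question.
- **Hyperfibrinolysis:** the time point is contradictory, not settled in favour of arrival. The loss ranges from none, if a sample taken after the regimen acts is used, to complete, if only samples before Bag B are used. The intermediate powers rest on assumed rates, an assumed halving and an equal three-way split. For INR the plan only needs to say which scheduled sample is used.

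The primary analysis and its sample size are untouched. This concerns a secondary aim, but it should be corrected because a literal reading of I.2 gives an uninformative test and the remedy is cheap.

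**What to change.** 1. In I.2 and J.3, state that the dose comparison uses the 12-hour-from-arrival values of EPL > 7.5%, INR > 1.4 and base deficit, as in Hypotheses 4A and 4C.
2. Reconcile the origin of the 12-hour sample (injury in I.3 and I.5, arrival in 4A and 4C) and its tolerance, so that the analysed sample follows the start of the regimen. Reconcile the 6-hour and 60-minute arrival TEG limits at the same time.
3. Define a 12-hour base deficit outcome, taken from blood gases already collected (N.3) or added to the existing 12-hour draw, with a stated time window.
4. Where the arrival value is documented as drawn before Bag B, use it as a baseline covariate: ANCOVA for continuous markers, a covariate in the J.3 logistic model. State how patients without a documented pre-Bag B value are handled.

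The cost is mainly wording, since TEG and INR are already scheduled. The main downside is missing 12-hour base deficit in patients without a blood gas near that time, unless it is added to the draw. Step 4 also needs the draw time and the Bag B start time to be recorded.
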